### 11.4.2. Liver Safety: Suggested Actions and Follow-up Assessments

#### Potential Cases of Drug-induced Liver Injury

Humans exposed to a drug who show no sign of liver injury (as determined by elevations in transaminases) are termed “tolerators,” while those who show transient liver injury but adapt are termed “adaptors.” In some participants, transaminase elevations are a harbinger of a more serious potential outcome. These participants fail to adapt and therefore are

“susceptible” to progressive and serious liver injury, commonly referred to as DILI. Participants who experience a transaminase elevation above  $3 \times \text{ULN}$  should be monitored more frequently to determine if they are “adaptors” or are “susceptible.”

Liver function test (LFT)s are not required as a routine safety monitoring procedure in this study. However, should an investigator deem it necessary to assess LFTs because a participant presents with clinical signs/symptoms, such LFT results should be managed and followed as described below.

In the majority of DILI cases, elevations in AST and/or ALT precede T bili elevations ( $>2 \times \text{ULN}$ ) by several days or weeks. The increase in T bili typically occurs while AST/ALT is/are still elevated above  $3 \times \text{ULN}$  (ie, AST/ALT and T bili values will be elevated within the same laboratory sample). In rare instances, by the time T bili elevations are detected, AST/ALT values might have decreased. This occurrence is still regarded as a potential DILI. Therefore, abnormal elevations in either AST OR ALT in addition to T bili that meet the criteria outlined below are considered potential DILI (assessed per Hy’s law criteria) cases and should always be considered important medical events, even before all other possible causes of liver injury have been excluded. In SCD, hyperbilirubinemia is due to a combination of acute hepatobiliary disease (ie, acute SC hepatic crisis, acute hepatic sequestration or acute intrahepatic cholestasis) as well as chronic hepatobiliary manifestations (ie, cholelithiasis, choledocholithiasis, and SCD cholangiopathy) (Shah, R 2017).

The threshold of laboratory abnormalities for a potential DILI case depends on the participant’s individual baseline values and underlying conditions. Participants who present with the following laboratory abnormalities should be evaluated further as potential DILI (Hy’s law) cases to definitively determine the etiology of the abnormal laboratory values:

- Participants with AST/ALT and T bili baseline values within the normal range who subsequently present with AST OR ALT values  $\geq 3 \times \text{ULN}$  AND a T bili value  $\geq 2 \times \text{ULN}$  with no evidence of hemolysis and an alkaline phosphatase value  $< 2 \times \text{ULN}$  or not available.
- For participants with baseline AST OR ALT OR T bili values above the ULN, the following threshold values are used in the definition mentioned above, as needed, depending on which values are above the ULN at baseline:
  - Preexisting AST or ALT baseline values above the normal range: AST or ALT values  $\geq 2$  times the baseline values AND  $\geq 3 \times \text{ULN}$ ; or  $\geq 8 \times \text{ULN}$  (whichever is smaller).
  - Preexisting values of T bili above the normal range: T bili level increased from baseline value by an amount of  $\geq 1 \times \text{ULN}$  or if the value reaches  $\geq 3 \times \text{ULN}$  (whichever is smaller).

Because knowledge of the total and unconjugated bilirubin, may suggest the treatment assignment, these measurements will be redacted to the Investigator and monitored on a

regular basis by an unblinded team. Rises in AST/ALT and T bili separated by more than a few weeks should be assessed individually based on clinical judgment; any case where uncertainty remains as to whether it represents a potential Hy's law case should be reviewed with the sponsor.

The participant should return to the investigator site and be evaluated as soon as possible, preferably within 48 hours from awareness of the abnormal results. This evaluation should include laboratory tests, detailed history, and physical assessment.

In addition to repeating measurements of AST and ALT and total bilirubin for suspected Hy's law cases, additional laboratory tests should include albumin, creatinine kinase, direct and indirect bilirubin, gamma-glutamyl transferase, PT/INR, eosinophils (%), and alkaline phosphatase. Consideration should also be given to drawing a separate tube of clotted blood and an anticoagulated tube of blood for further testing, as needed, for further contemporaneous analyses at the time of the recognized initial abnormalities to determine etiology. A detailed history, including relevant information, such as review of ethanol, acetaminophen/paracetamol (either by itself or as a coformulated product in prescription or over-the-counter medications), recreational drug, or supplement (herbal) use and consumption, family history, sexual history, travel history, history of contact with a jaundiced person, surgery, blood transfusion, history of liver or allergic disease, and potential occupational exposure to chemicals, should be collected. Further testing for acute hepatitis A, B, C, D, and E infection, total bile acids, liver imaging (eg, biliary tract), and collection of serum samples for acetaminophen/paracetamol drug and/or protein adduct levels may be warranted.

All cases demonstrated on repeat testing as meeting the laboratory criteria of AST/ALT and total bilirubin elevation defined above should be considered potential DILI (Hy's law) cases if no other reason for the LFT abnormalities has yet been found. **Such potential DILI (Hy's law) cases are to be reported as SAEs, irrespective of availability of all the results of the investigations performed to determine etiology of the LFT abnormalities.**

A potential DILI (Hy's law) case becomes a confirmed case only after all results of reasonable investigations have been received and have excluded an alternative etiology.

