### 3.2. Benefit/Risk Assessment

#### 3.2.1. Risk Assessment

Based on the experience with osivelotor at the time of this Protocol Amendment, no participant has experienced any adverse reaction of clinical significance. The theoretical potential risk for osivelotor is decreased oxygen delivery, however there are no current adverse events attributed to the study drug that support this theoretical risk.

Potential Risk of Clinical Significance	Summary of Data/Rationale for Risk	Mitigation Strategy
Study Intervention Osivelotor (PF-07940367 or GBT021601)		
Decreased oxygen delivery	Increased oxygen affinity associated with the osivelotor mechanism has a theoretical potential to result in decreased oxygen delivery	Close monitoring of AEs through TME monitoring, vital signs, EPO levels, and hemoximetry Planned near infrared spectroscopy (NIRS) study to assess evidence of organ preservation designed to address this risk.
Study Procedures		

Potential Risk of Clinical Significance	Summary of Data/Rationale for Risk	Mitigation Strategy
Worsening anemia in participant with underlying sickle cell anemia.	Frequent blood samples will be collected from anemic participants during the study which may result in potential loss of blood volume in already anemic participants	A reduced PK sampling scheme is incorporated for pediatric participants so as not to exceed blood draw limits (0.8 mL/kg in a given 24-hour period; 2.4 mL/kg in a given 4-week period). Collection kits that limit blood volume draws are being used for pediatric participants. Investigators are allowed to limit blood sample collection in consideration of patient condition, with the guidance of a sample priority list (Table 10). Blood volume limits are following guidelines included in EU guidance for ethical considerations for clinical trials conducted with minors. Best practices for pediatric blood collection are provided in Section 9.3.3.1.
Potential DDI	Based on preliminary in vitro data, osivelotor has the potential to interact with CCI [REDACTED]	Close monitoring of the Prohibited/Restricted medication list

Adult participants in this study who have completed Part A of C5351004 (with open label osivelotor treatment), or any other open label osivelotor study, will be assessed every 12 weeks for safety and response to treatment.

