### 3.3. Study Rationale

This is a multicenter, global, open-label extension study to evaluate the long-term safety, tolerability and SCD related complications of participants who have been treated with osivelotor. Gathering more patient-years of exposure to osivelotor will allow the Sponsor to further understand and characterize the safety profile of osivelotor.

All participants in this study are participants with SCD who have previously participated in an osivelotor clinical study. Participation in this study will provide continued access to

treatment until the participant has access to osivelotor from an alternative source (eg, through commercialization, a managed-access program, or a Sponsored initiative) or until the Sponsor decides to terminate the Study. Some participants in this study will have received osivelotor or placebo in a prior study in a blinded fashion and therefore this study will evaluate the first exposure to osivelotor in some participants. As such, the safety of initial exposure to osivelotor will also be evaluated in this study.

The daily maintenance dose for adult participants entering the study will be 150 mg osivelotor, which is the optimal dose selected from Part A of C5351004. The daily maintenance dose for all adult participants who have already enrolled into C5351005 prior to this amendment may be adjusted to the selected dose of 150 mg. Adolescent and pediatric participants from C5351004 Parts B and C will be administered a dose that provides generally equivalent exposure to adult participants.

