## 5.2. Scientific Rationale for Study Design

This study is an open-label study to evaluate the safety of long-term administration of osivelotor without a comparator. Participants in this study will have participated in a controlled clinical trial of osivelotor (originating study) in which they will have received osivelotor or placebo. Given the long half-life of osivelotor at the dose to be evaluated in this study, most of the participants are expected to maintain target concentrations throughout the study.

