## **7.3. Randomization and Blinding**

This is an open-label study. Randomization and blinding are not applicable.

As this is an open-label, long-term extension study, the sponsor may conduct unblinded reviews and/or summaries of the data during the course of the study for the purpose of safety assessment, supporting clinical development, and/or supporting regulatory review.

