**2.2.3. Study Design**

C5351005 (OLE) is designed as a multicenter, global, open-label extension study. The primary objective is to assess the long-term safety of osivelotor in participants with SCD. This study is available to eligible participants who have previously enrolled in a Pfizer-sponsored osivelotor clinical study and meet the entry criteria for this study.

Eligible participants will receive open-label osivelotor at Baseline (Day 1). It is intended that Day 1 coincides with the final visit from the originating osivelotor study. End of Treatment (EOT) assessments from the originating study will serve as Baseline assessments for this study. If Day 1 for this study is greater than 7 days from the completion of the originating study, new baseline assessments will be obtained. If during the period between Day 1 of this study and completion of the originating study no dose is received for greater than 3 consecutive days, an appropriate loading dose will be administered prior to continued maintenance dosing.

Only participants from C5351004 Part A (also referred to as the “parent study”) were enrolled into the OLE. C5351004 Part A is a study which enrolled only adult participants. There are two sets of participants rolling over from C5351004 Part A to the OLE study – (i) participants without a delayed start (Date of first dose in C5351005 – EOT date from C5351004 + 1 ≤ 42 days) and (ii) participants with a delayed start of OLE (Date of first dose in C5351005 – EOT date from C5351004 + 1 > 42 days). Each set follows a distinct schedule of assessments as outlined in the C5351005 protocol.

**3. ENDPOINTS AND BASELINE VARIABLES: DEFINITIONS AND CONVENTIONS****3.1. Primary Endpoint(s)****3.1.1. Incidence of TEAEs**

A treatment-emergent adverse event (TEAE) is defined as an AE that occurs during the effective duration of treatment defined as the time from the first dose of study drug through last dose of study drug + 56 days.

TEAEs that occur in the parent study are not counted as TEAEs in this study. In case, the start date of AE is the same date as the treatment start date and the question in the AE CRF page “Is this AE continuing from the parent study?” = “Yes”, then the event is not a TEAE,

as long as it can be confirmed that the AE in question had a start date in the parent study and no end date in the parent study.

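### Protocol 11.4.2 withholds total and unconjugated bilirubin from every Investigator in an open-label study, with no deadline for alerting the site to a potential Hy's-law case

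*Protocol*

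**What the plan says.** Protocol 11.4.2 (Appendix 2, liver safety) states: "Because knowledge of the total and unconjugated bilirubin, may suggest the treatment assignment, these measurements will be redacted to the Investigator". The rest of that sentence gives the monitoring of these values to an unblinded team. It sets no review interval, alert threshold or time limit for contacting the site.

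The same section defines a potential Hy's-law case by AST or ALT together with total bilirubin, in the absence of hemolysis and with alkaline phosphatase below 2 times ULN or not available. It asks for repeat AST, ALT and total bilirubin, plus direct and indirect bilirubin, in suspected cases. It says of potential cases that such "cases are to be reported as SAEs, irrespective of availability of all the results of the investigations performed to determine etiology" of the abnormalities.

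On design, Protocol 7.3 says: "This is an open-label study. Randomization and blinding are not applicable". Protocol 5.2 says: "This study is an open-label study to evaluate the safety of long-term administration of osivelotor without a comparator". Protocol 3.3 notes that "Some participants in this study will have received osivelotor or placebo in a prior study in a blinded fashion". The SAP (2.2.3) reports who came in: "Only participants from C5351004 Part A" were enrolled. Protocol 3.2.1 describes Part A treatment as open label.

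**The concern.** The redaction is justified by a treatment assignment that has to stay hidden, and this study has none. Total bilirubin, however, is the value that separates a potential Hy's-law case from an isolated transaminase rise. If the treating Investigator does not see it, recognition depends on another party who is under no stated time limit.

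The two time limits that might help both run from awareness: re-evaluation, preferably within 48 hours (11.4.2), and SAE reporting within 24 hours (9.4.8). Redaction can delay awareness itself. For participants without a delayed start, scheduled chemistry after baseline is every 12 weeks (Table 2), so a result that nobody acts on may not be followed by another scheduled one for some time.

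**Working it through.** There is no plan figure to reproduce. The check compares the sections and then works out which cases the remaining rules miss.

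**Step 1. Does the stated reason apply?**

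| Group | Blinded assignment to protect? | Covered by the redaction? |
|---|---|---|
| This study | No: open label, osivelotor for all (7.3, 5.2) | Yes |
| Rollovers from blinded Part B | Possibly, while the parent study is blinded (3.3) | Yes |
| Rollovers from Part A, the only group enrolled (SAP 2.2.3) | No: open label, although at several dose levels (3.2.1, Table 13) | Yes |

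**Step 2. Can the Investigator apply 11.4.2?** The AST/ALT thresholds can be read without bilirubin. The combined case definition cannot, because it requires total bilirubin. Direct bilirubin is not named in the redaction, but it gives only a lower bound on the total. Protocol 9.3.3 has the Investigator assess all out-of-range values and allows extra tests. Neither section says whether the redaction reaches tests ordered by the site.

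**Step 3. Which cases does the bilirubin-free rule in 11.4.1 miss?** Values are in multiples of ULN. Assume no hemolysis and alkaline phosphatase below 2 or not available.

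- 11.4.1, SAE if unexplained: ALT > 4 or AST > 3.
- 11.4.2 enzyme threshold: 3 if baseline is normal; otherwise min(max(2 × baseline, 3), 8).
- 11.4.2 bilirubin threshold: 2 if baseline is normal; otherwise min(baseline + 1, 3).

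Gap for ALT, with AST at 2.5 from a normal baseline and the bilirubin criterion met:

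| ALT baseline | Lowest ALT meeting 11.4.2 | ALT range missed by 11.4.1 |
|---|---|---|
| up to 1.0 | 3.0 | 3.0 to 4.0 |
| 1.5 | max(3.0, 3) = 3.0 | 3.0 to 4.0 |
| 1.6 | 3.2 | 3.2 to 4.0 |
| 1.8 | 3.6 | 3.6 to 4.0 |
| 2.0 | 4.0 | 4.0 only |
| 2.1 | 4.2 | none |

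For AST alone, a baseline up to 1.5 needs at least 3.0 under 11.4.2 against more than 3 under 11.4.1, so the gap is exactly 3.0. At baseline 1.6 the requirement is 3.2 and there is no gap.

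Bilirubin thresholds by baseline: 1.0 gives 2.0; 1.5 gives 2.5; 1.8 gives 2.8; 2.0 gives 3.0; 2.5 gives min(3.5, 3) = 3.0.

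Two participants inside the gap, both with ALT 3.5, AST 2.5, normal AST/ALT baselines and no hemolysis:

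- Bilirubin 1.8 rising to 2.9: threshold 2.8, so 11.4.2 is met.
- Bilirubin 2.0 rising to 2.5: threshold 3.0, so 11.4.2 is not met.

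Neither meets 11.4.1, and the missing total bilirubin is what separates them. Outside the gap the rules overlap: ALT 5 with bilirubin 1.0 rising to 2.5 meets 11.4.2 (2.5 ≥ 2.0) and the enzyme limit in 11.4.1 (5 > 4).

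**The case against.** **The redaction had a possible purpose.** The protocol, dated February 2024, planned rollovers from placebo-controlled Part B (3.3, Table 3) while the parent study was ongoing. Protocol 3.1 reports that indirect bilirubin improved on drug, so a change after rollover could hint at the parent-study arm. This stands. A reader might infer that the rule never had any basis, but the documents do not support that. The SAP statement that only Part A participants enrolled dates from June 2025 and does not show that the 2024 expectation was unreasonable. What can be criticised is that the rule was not limited to those participants. Table 7 also describes the supply as blinded, but this conflicts with 7.3 and creates no assignment.

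**Sites keep most liver signals.** This also stands. Table 8 starts repeat testing from ALT 3 times ULN. It calls for a dose hold and Medical Monitor contact when ALT above 3 times ULN comes with raised conjugated bilirubin, jaundice, raised INR or symptoms. Urine bilirubin is in Table 9. The 11.4.1 SAE rule and SAE reporting on judgment (9.4.2) do not need the redacted values. 11.4.2 also sends to the sponsor "any case where uncertainty remains as to whether it represents a potential" Hy's-law case. None of these sets a deadline for the team that holds the values. The SAP 6.5.6 listing is an analysis output, not real-time protection.

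**Hemolysis narrows the gap.** The case definition requires its absence, and Protocol 3.1 describes sickle cell disease as marked by hemolytic anemia. Read literally, many participants may not qualify whatever their bilirubin. This limits the size of the problem and does not remove the contradiction.

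**It may be template text.** 11.4.2 also says liver tests are not routine, although the schedule includes chemistry. Carry-over from a blinded protocol is plausible but unproven, and sites must follow the text as it stands. The tension with 9.3.3 could be read as a specific exception to a general rule.

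**Conclusion.** The rule is wrong as written and should be fixed. It applies a blinding safeguard to all participants in an open-label study, including the open-label Part A group, for whom it protects nothing. It stops Investigators from applying the combined 11.4.2 case definition to redacted central-laboratory reports, and it sets no deadline for alerting them.

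The loss is delayed site recognition of a potential Hy's-law case. The SAE-reporting gap is narrow. With normal AST/ALT baselines it is ALT 3 to 4 times ULN with AST at most 3 times ULN. It shrinks as the ALT baseline rises above 1.5 times ULN and disappears above 2.0. It exists only when hemolysis is absent and the alkaline phosphatase condition is met.

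A reader might go further and infer that liver monitoring fails, or that cases were missed. The documents support neither: other triggers remain, no event rate can be derived, and nothing shows whether the redaction was switched on. The contradiction in the text is certain; its practical effect is not.

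**What to change.** Delete the sentence in Protocol 11.4.2 on redaction and the unblinded team, so that sites receive total and unconjugated bilirubin from the central laboratory. If participants from a still-blinded parent study could yet enrol, limit the redaction to them and require immediate notification of the Investigator when an 11.4.2 threshold is crossed.

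The cost is one sentence of protocol wording, by amendment or administrative letter, plus a central-laboratory reporting setting if the redaction was active. No hypothesis test or planned analysis is affected. If enrolment or dosing has ended, the sponsor should still confirm whether results were redacted and whether sites were told of any participant who crossed a threshold.

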## 11.5. Appendix 3: Kidney Safety Monitoring Guidelines

### 11.5.1. Laboratory Assessment of Change in Kidney Function and Detection of Kidney Injury

Standard kidney safety monitoring requires assessment of baseline and postbaseline Screat measurement to estimate kidney function [Screat-based eGFR] or creatinine clearance [eCrCl]. Baseline and postbaseline Scys makes it feasible to distinguish AKI from other causes of Screat increase. If Screat increase is confirmed after baseline, then reflex measurement of Scys is indicated.

**ADULTS:** Currently, 2021 CKD-EPI eGFR equations (Screat-only based and combined Screat plus Scys-based) are valid for use in adults only. At baseline Screat and Scys values are needed to calculate 2021 CKD-EPI eGFR by Screat-only based equation (see Table in Section 11.5.2.1) and by combined Screat plus Scys-based equation. When post-baseline Screat increase  $\geq 0.3$  mg/dL is confirmed, then reflex Scys measurement is needed to enable post-baseline comparison of eGFR changes (Screat-only based eGFR and combined Screat plus Scys eGFR).

**PEDIATRICS:** Currently, no Screat plus Scys eGFR equations have been universally adopted for pediatrics. Therefore, comparison of baseline Screat and Scys to post-baseline Screat and reflex Scys are utilized to support differentiation of AKI from DICI.

Regardless of whether kidney function monitoring tests are required as a routine safety monitoring procedure in the study, if the investigator or sponsor deems it necessary to further assess kidney safety and quantify kidney function, then these test results should be managed and followed per standard of care.

